3.3 Clinical Trial Participation Status of Subjects and Protocol Violation

The table of clinical trial participation status of subjects (mITT, PP, and safety analysis groups), reasons for early withdrawal, and the distribution of the clinical trial protocol violations will be presented.

3.4 Demographic Characteristics and Characteristics Prior to Administration of Study Drug

As a way to check significant differences in demographic and clinical characteristics between the two arms prior to administration of study drugs, the serial data is summarized into mean, standard deviation, median, minimum, and maximum values, and the two arm are compared by an independent t-test or the Wilcoxon rank sum test. For categorical variables, the frequency and proportion per group is found and the two arms are compared by Chi-square test or Fisher's exact test. This analysis is performed for the ITT analysis group.

The following items will be evaluated for the subjects' characteristics prior to administration of the study drug and presented for each randomized arm.

Type	Endpoints
Enrollment of each site and randomization stratification factor	- To summarize the frequency and proportion of randomization per each site, stratification factor (presence/absence of cavitation on baseline chest radiographs, presence/absence of baseline diabetes mellitus)
Demographic characteristics and vitality signs	- Age, gender, height, weight, blood pressure, and pulse
Past history	- Past history of tuberculosis and the number of treatments - Diabetes mellitus, optic neuropathy, or peripheral neuropathy

	
 - Galactose intolerance, Lapp lactase deficiency, and glucose-galactose malabsorption - Other diseases
Medication history	
 - Other medication except for TB medication or use of prohibited medication while on study drug
Physical/neurological examination	
 - Physical examination result and neurological examination result
Drug susceptibility test	
 - Screening visit: Xpert MTB/RIF assay (MTB and RIF resistance), MTBDRsl (fluoroquinolone resistance and XDR-TB), resistance, and resistant drug - Baseline visit: Resistance and resistant drug
Sputum AFB smear and CXR (Chest CT)	
 - Sputum AFB panel (AFB smear, solid culture, liquid culture) - CXR (range of lesions and presence or absence of cavity), Chest CT (range of lesions and presence or absence of cavity)
HIV/HBV test	
 - HIV test and HBV test result
Chemistry/Electrolyte/Complete blood count	
Chemistry
 
 - T-bilirubin, alkaline phosphatase, BUN, AST, ALT, creatinine, calcium, phosphorus, uric acid, glucose, cholesterol, protein, and albumin 
Electrolyte
 
 - Sodium, potassium, and chloride 
Complete blood count
 
 - WBC, ANC, hemoglobin, and PLT
Urine HCG/ECG/Optic Test (Ishihara Color Plate)	
Urine HCG
 
 - Performance and result 
ECG
 
 - Performance and result, Rhythm, QTcF 
Optic test (Ishihara Color Plate)
 
 - Performance and the number of correct answers of 24 Ishihara color plates

3.5 Adherence Assessment

- The study coordinator checks the study drug adherence by comparing the drug package with residual pill count at each visit.

In the event that a scheduled visit is changed, the study coordinator checks administration status of the study drug and other medication during that period as well.

- Drug Adherence by each drug = (actual dosing day/ prescribed dosing day) * 100

- Final Adherence = Average value of medication adherence by each drug

In this case, the prescribed dosing day is defined as the sum of the prescribed dosing days for the entire period and the actual dosing day is defined as the total of the actual dosing days for the entire period, and the Final Adherence is defined as the average value of the Drug Adherence by each drug.

The Adherence to study drug and throughout the total treatment period of both arms is summarized with the final adherence and by each drug taken, with the mean, standard deviation, median and minimum and maximum value, and the final adherence will be compared between the two arms by conducting an independent t-test or Wilcoxon rank sum test.

3.6 Efficacy Evaluation

All statistical analysis of the two arms is carried out at a significance level of 5% for both sides unless stated otherwise. For additional analysis, a stratified analysis is performed for primary and secondary outcomes evaluation by stratification into sputum smear positive patient groups and sputum smear negative patient groups based on the sputum smear microscopy results.

3.6.1 Primary Efficacy Evaluation

The primary outcome of this clinical trial is the treatment success rate at 24 months after the initiation of treatment (**based on the results of liquid culture**). It describes the treatment success rate of the control arm and the investigational arm with a two-sided 95% confidence interval. Then, in order to tests for non-inferiority of the investigational arm, when the lower limit of one-sided 97.5% confidence interval of the difference ($P_I - P_C$) between control and investigational arm is larger than the non-inferiority margin of -10%, it is concluded that the treatment success rate of the investigational arm is non-inferior to the treatment success rate of the control arm. The subjects whose treatment result is assessed as 'Not accessible' are excluded from the primary outcome evaluation.

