10.1. Sample size justification

The hypothesis of this study is that the treatment success rate at 24 months after the initiation of treatment for MDR TB using the new regimen including new anti-TB drugs will not be inferior to conventional treatment regimens. (Non-inferiority test)

Presumptions when calculating sample size are as follows.

- 1) Level of significance, $\alpha = 0.025$ (one-sided test)
- 2) Type 2 error (β) set at 0.20 to maintain 80% for power of the test
- 3) Subject no. ratio (control arm : investigational arm) = 1 : 1
- 4) Primary outcome: treatment success rate at 24 months after the initiation of treatment
- 5) The hypothesis of the study is as follows.
 - ① Null hypothesis: Four drug regimen treatment success rates at 24 month are inferior to conventional treatment outcomes. ($H_0 : P_T - P_C \leq \delta$)
 - ② Alternative hypothesis: Four drug regimen treatment success rates at 24 month are not inferior to conventional treatment outcomes. ($H_1 : P_T - P_C > \delta$)

Based on the study result of Kwak et al, 'Changes in treatment outcomes of multidrug-resistant tuberculosis, Int J Tuberc Lung Dis 19(5):525-530'(3), presuming 24 month treatment success rate of control arm as 80% and 24 month treatment success rate of investigational arm as 90%, the non-inferiority margin (δ) is -0.10 which is regarded as non-inferior when the difference is less than 10% between the two arms. The number of study subjects is 48 per arm.

In addition, reflecting 1) proportion of fluoroquinolone-susceptible MDR-TB among participants with positive Xpert MTB/RIF assay of 50%, and 2) anticipating 5% lost to follow-up, the final number of participants is calculated as $N/(0.50*0.95)$ resulting in 102 persons per arm, 204 in total.

If a participant withdrew for any reasons within two weeks after enrollment, the participant will be replaced. Considering the number of replaced participants, the enrollment accrual ceiling is 220 persons maximum.

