10.2. Statistical Analysis Method

1) Analysis Group Definition

Data obtained from subjects through clinical trials will be analyzed by mITT (Modified Intention-To-Treatment) analysis and PP (Per-Protocol) analysis. Efficacy evaluation will be based on a mITT (Modified Intention-To-Treatment) and additional analysis on PP (Per-Protocol) group. Safety analysis will be performed on the safety group.

- The mITT (Modified Intention-To-Treatment) group includes participants who are randomized after satisfying eligibility criteria and receive study drugs at least one time.
- The PP (Per-Protocol) group includes participants that satisfy the following among mITT group.
 - 1) When completing over 80% of the planned treatment (in other words, for control arm, 64 weeks or longer treatment; For investigational arm, 32 weeks or longer treatment in the 9-month treatment group and 42 weeks or longer treatment in the 12-month treatment group)
 - 2) Participants who completed the study per protocol during the clinical trial period.
- The Safety analysis group includes participants who receive study drugs at least one time.

2) Handling of Missing Data

When categorized as 'loss to follow-up', 'withdrawal', or 'withdrawal of consent', it is deemed as following.

- ① 'Treatment failure' in the case of dropping out due to 'loss to follow-up', 'investigator's decision', 'withdrawal of consent', 'treatment failure', or 'death' during the treatment
- ② 'Not accessible' in the case of dropping out due to pregnancy during the treatment
- ③ 'Treatment failure' in the case of dropping out due to 'relapse' after the treatment completion
- ④ 'Not accessible' when there is no evidence of treatment failure, such as bacteria reversion in the case of withdrawal due to 'loss to follow-up', 'investigator's decision', 'withdrawal of consent', 'pregnancy', or 'death' after the treatment completion

3) Basic Characteristics Analysis of Subjects Prior to Administration of Study Drugs

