3.1 General Principle of Result Analysis

Data obtained from subjects through clinical trial will be analyzed by mITT (modified Intention-To-Treatment) analysis and PP (Per-Protocol) analysis. Efficacy evaluation will be based on a mITT (modified Intention-To-Treatment) and additional analysis on PP (Per-Protocol) group. Safety analysis will be performed on mITT, PP and the safety group (study drug administration group).

Subject Group	Definition
mITT	
- The mITT group includes participants who are randomized after satisfying eligibility criteria and receive study drugs at least one time. The subjects are not confirmed to be additionally resistant to fluoroquinolone, mono-resistant to rifampicin, or susceptible to rifampicin.

PP	
The PP (Per-Protocol) group includes participants that satisfy the following among the mITT group.
 
When completing over 80% of the planned treatment
 
: For control arm, 64 weeks or longer treatment; For investigational arm, 32 weeks or longer treatment in the 9-month treatment group and 42 weeks or longer treatment in the 12-month treatment group

Safety	
Participants who completed the study per protocol during the clinical trial period
 
: More than 80% of the planned period before treatment is completed, the following cases are considered protocol violation and excluded from the analysis group
 
① withdrawal or death.② The sputum test before culture conversion was not conducted③ Administration of study drug in the control arm 
The Safety analysis group includes participants who have taken study drugs at least one time.
 
: Evaluation based on the administration of study drug (delamanid or linezolid)

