5.1 Primary Efficacy Evaluation Results

5.1.1 Treatment Success Rate at 24 Months after the initiation of treatment

- The analysis presents the frequency and proportion of treatment success rate after 24 months of each arm to check if the treatment success rate of the investigational arm 24 months after the initiation of treatment is inferior to the control arm. It presents the 95% confidence interval of the treatment success rate difference (investigational arm's treatment success rate - control arm's treatment success rate) 24 months after the initiation of treatment. The one-sided test is performed at the significant level of 2.5% using the lower limit of the 95% confidence interval about the difference of the treatment success rate between the two arms. If the lower limit of the confidence interval is larger than 0.1, it proves that the treatment success rate of the investigational arm is inferior to the control arm. If it is equal to or less than 0.1, it cannot prove that the investigational arm is not inferior to the control arm (Table 15).

Table 15. Treatment Success Rate at 24 Months after the initiation of treatment

	Investigational Arm	Control Arm	All
mITT analysis group	xx	xx	xx
Not assessable ²⁾	xx	xx	xx
Treatment success rate at 24 months after the initiation of treatment, n (%)	xx (xx.xx)	xx (xx.xx)	xx (xx.xx)
Difference [95% CI]	xx.xx[xx.xx, ∞] ¹⁾		
Treatment failure, n (%)	xx (xx.xx)	xx (xx.xx)	xx (xx.xx)
PP analysis group	xx	xx	xx
Not assessable ²⁾	xx	xx	xx
Treatment success rate at 24 months after the initiation of treatment, n (%)	xx (xx.xx)	xx (xx.xx)	xx (xx.xx)
Difference [95% CI]	xx.xx[xx.xx, ∞] ¹⁾		
Treatment failure, n (%)	xx (xx.xx)	xx (xx.xx)	xx (xx.xx)

Sub-group analysis	XX	XX	XX
1-1. Sputum smear positive ³⁾	XX	XX	XX
mITT analysis group	XX	XX	XX
Not assessable ²⁾	XX	XX	XX
Treatment success rate at 24 months after the initiation of treatment, n (%)	xx (xx.xx)	xx (xx.xx)	xx (xx.xx)
Difference [95% CI]	xx.xx[xx.xx, ∞] ¹⁾		
Treatment failure, n (%)	xx (xx.xx)	xx (xx.xx)	xx (xx.xx)
PP analysis group	XX	XX	XX
Not assessable ²⁾	XX	XX	XX
Treatment success rate at 24 months after the initiation of treatment, n (%)	xx (xx.xx)	xx (xx.xx)	xx (xx.xx)
Difference [95% CI]	xx.xx[xx.xx, ∞] ¹⁾		
Treatment failure, n (%)	xx (xx.xx)	xx (xx.xx)	xx (xx.xx)
1-2. Sputum smear negative ⁴⁾	XX	XX	XX
mITT analysis group	XX	XX	XX
Not assessable ²⁾	XX	XX	XX

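### Minor improvement, not an error: the primary non-inferiority interval states no use of the randomisation strata (cavitation, diabetes), although the SAP's mITT set drops participants after randomisation and so keeps only part of the block balance

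*Combined protocol and SAP*

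**What the plan says.** Protocol 8.2 randomises 1:1 in blocks of 4 or 6, stratified by cavitation and diabetes. SAP 3.4 lists the same factors for the baseline summary: "presence/absence of cavitation on baseline chest radiographs, presence/absence of baseline diabetes mellitus". In the SAP they appear only in baseline and enrolment tables.

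The primary decision (protocol 10.2 item 4, SAP 3.6.1) is taken "when the lower limit of one-sided 97.5% confidence interval of the difference" in success rates exceeds -10%. SAP 5.1.1 adds: "The one-sided test is performed at the significant level of 2.5% using the lower limit of the 95% confidence interval". None of these places mentions strata or covariates, or names an interval method.

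Two other breakdowns of the primary outcome are planned. One is "stratification into sputum smear positive patient groups and sputum smear negative patient groups" (SAP 3.6); the other is by pyrazinamide resistance (SAP 3.6.2 and 5.2.7). Neither is a randomisation factor.

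The protocol's mITT set "includes participants who are randomized after satisfying eligibility criteria and receive study drugs at least one time". SAP 3.1 uses the same definition and adds: "The subjects are not confirmed to be additionally resistant to fluoroquinolone, mono-resistant to rifampicin, or susceptible to rifampicin". The sample-size sections (protocol 10.1, SAP 2.3) assume a "proportion of fluoroquinolone-susceptible MDR-TB among participants with positive Xpert MTB/RIF assay of 50"%. They also replace anyone who withdraws within two weeks of enrolment, up to a ceiling of 220.

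**The concern.** Stratified blocks normally keep the arms balanced on the chosen factors whatever analysis follows. Here that protection is weakened, because participants leave the SAP's mITT set after allocation, and they leave without regard to blocks. If cavitation or diabetes affects treatment success, a chance imbalance among those who remain moves the unadjusted difference up or down.

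On the planning assumptions only about 48-51 participants per arm carry the test, and the trial is open-label. A result near the margin could be disputed because one arm happened to have fewer cavities. Answering that dispute with an adjusted analysis chosen after the data are seen would be weak. Naming the analysis in advance settles it.

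**Working it through.** **1. The plan's own figure.** Inputs from SAP 2.3: success 80% control and 90% investigational, margin 10 points, one-sided 2.5%, power 80%.

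n per arm = (1.960 + 0.842)² × (0.8×0.2 + 0.9×0.1) / (0.10 + 0.10)² = 7.849 × 0.25 / 0.04 = 49.06, so 50 when rounded up. The plan states 48, where power is 79.1% by the same formula; this is close enough. Inflation: 48/(0.50×0.95) = 101.05, so 102 per arm and 204 in total, as stated.

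Analysed per arm: 102×0.50 = 51, or 102×0.475 = 48. Standard error of the difference at 51 per arm: √(0.25/51) = 0.070, or 7 points.

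**2. How much balance is lost.** Let p be cavitation prevalence (assumed 50%), k the fraction retained, and n = 102k. If removal is random, the variance of the between-arm difference in cavitation is about 2p(1-p)(1-k)/n. To this add 0.01² for the small imbalance left by incomplete blocks (the simulated SD as randomised is 0.010).

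- k = 0.50: √(2×0.25×0.50/51 + 0.0001) = 0.071. Chance of a difference above 10 points: 16%.
- k = 0.75: √(2×0.25×0.25/76.5 + 0.0001) = 0.042. Chance: 1.6% (simulated 1.8%).
- k = 0.95: 0.019. Chance: practically zero.

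**3. Effect on the test.** Simulated trials: 204 participants in permuted blocks of 4 or 6 within four strata, each retained at random with probability 0.5 and no replacement. Assumed, not in the documents: cavitation 50%, diabetes 25%, and one odds ratio (OR) for success applied to both factors. Truth is 90% vs 80% for power and 70% vs 80% for type I error. Miettinen-Nurminen score limits are used for both analyses; there are 1,000,000 trials per setting. Changes are computed before rounding.

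| OR per factor | Power, unstratified | Power, stratified | Change (points) | Verdicts differ |
|---|---|---|---|---|
| 1 | 79.6% | 78.9% | -0.7 | 2.8% |
| 0.5 | 79.7% | 79.5% | -0.1 | 3.8% |
| 0.33 | 80.0% | 80.7% | +0.8 | 5.0% |
| 0.25 | 80.2% | 81.9% | +1.7 | 6.0% |

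Overall type I error is 2.1-2.5% unstratified and 2.3-2.5% stratified. With 75% retained the power change is -0.2 to +0.9 points; with 95% retained it is 0.0 to +0.3.

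**4. Trials with a cavitation difference above 10 points (8% in each direction).** Values are for OR 0.5, 0.33 and 0.25.

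| Investigational arm has | Type I error, unstratified | Stratified | Power, unstratified | Stratified |
|---|---|---|---|---|
| fewer cavities | 3.6, 4.2, 4.4% | 2.4-2.5% | 83.6, 85.7, 86.9% | 78.8, 79.7, 80.8% |
| more cavities | 1.4, 1.0, 0.8% | 2.3-2.4% | 74.6, 72.5, 70.9% | 78.4, 79.7, 80.6% |

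Over both directions together, type I error is 2.5-2.6% unstratified and 2.4-2.5% stratified. A 10-point imbalance shifts the unstratified difference by 0.8, 1.3 and 1.5 points, against the standard error of 7.

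**5. Type of limit, separately.** In the order OR 1, 0.5, 0.33, 0.25, unstratified Wald limits give power 82.2, 82.3, 82.6, 82.9% and type I error 2.7, 2.6, 2.4, 2.3%. Score limits cost about 2.6 points of power against them. The Mantel-Haenszel difference with Sato (Wald-type) variance gives power 81.7, 82.6, 84.2, 85.7% and type I error 2.7-2.8%.

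**The case against.** The strongest reply is that both analyses are valid and the choice between them is close to preference. The average gain is below 2 points of power and is negative unless the factors are strongly prognostic. That stands, and it is why the point is minor.

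Four stronger readings are tempting, and the documents do not support them.

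- **That the unstratified test inflates type I error.** The 3.6-4.4% figures apply only to the 8% of simulated trials imbalanced in one direction. The opposite 8% are conservative, and the two offset.
- **That half the participants will be lost.** Half is an upper planning figure. Protocol 5.5 excludes known fluoroquinolone resistance, protocol 8.1 allows genotypic testing at screening, and entry is not limited to Xpert-positive patients (protocol 5.4). Resistance findings are withdrawal reasons (protocol 8.7), so cases found within two weeks can be replaced. The protocol's own mITT definition states no such removal.
- **That the plan rules out stratification.** It is silent on the interval method altogether.
- **That the label in SAP Table 2 (CXR or chest CT) is wrong.** Protocol 8.2 and SAP 3.4 name chest radiographs for the stratum. But protocol 8.1 lets chest CT stand in for CXR, and SAP 3.4 and Table 8 also record cavities on CT. The texts differ, and nothing in them shows which source defined the stratum.

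**Conclusion.** The point holds as a cheap, minor improvement. The plan balances on two factors and then states no use of them for its main question, while the SAP's mITT set weakens the balance. The unstratified analysis is not an error.

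The benefit is mainly conditional: with a stratified estimate, the error rate stays near 2.5% whichever arm has more cavities. On average, stratifying changes power by -0.7 to +1.7 points with half retained, and by less as more are retained. The figures rest on assumed prevalences, on equal odds ratios for both factors, and on removal unrelated to arm. The last is plausible because resistance found at entry is a baseline property, but it is not guaranteed in an open-label trial. At 30% cavitation and 15% diabetes the power changes are similar (about -0.8 to +1.7), and 13% of trials are imbalanced by more than 10 points.

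A reader might infer that stratifying repairs the post-randomisation exclusions. It does not: any selection they cause remains.

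**What to change.** In SAP 3.6.1, SAP 5.1.1 and protocol 10.2 item 4:

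- Make the primary mITT interval a Mantel-Haenszel-weighted risk difference over the four cavitation-by-diabetes strata as entered at randomisation.
- State in advance that the strata collapse to cavitation alone if any stratum has participants in only one arm. With half retained this happens in 0.2% of simulated trials at 50%/25% prevalence and in 12.6% at 30%/15%.
- Use the same method for the PP interval. Leave the smear and pyrazinamide subgroup intervals unstratified, where strata would be sparse.
- Keep the unstratified difference as a sensitivity analysis.
- Name the type of limit as a separate decision. Score limits hold 2.5%, at about 2.6 points of power against Wald. Sato variance keeps that power, with type I error of 2.7-2.8%.
- Reconcile protocol 8.1 and 8.2, SAP 3.4, and SAP Tables 2 and 8 on the source of the cavitation stratum, without presuming which is right.

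The cost is wording and a few lines of code, with no new data and no change in sample size. The downside of stratifying is about 0.7 points of power if neither factor is prognostic. If score limits are also adopted, the combined loss against unstratified Wald is 3.4, 2.7, 1.9 and 1.0 points at OR 1, 0.5, 0.33 and 0.25. If few participants are removed from mITT, there is little to gain.

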3.6.2 Secondary Efficacy Evaluation

- ① Time to sputum culture conversion¹ after the initiation of treatment (liquid and solid culture media)
- ② Sputum culture conversion proportion at two months of treatment (liquid and solid culture media)
- ③ Sputum culture conversion proportion at six months of treatment (liquid and solid culture media)

¹ The definition of 'culture conversion to negative' is per the protocol section '6. Definition'. Contamination after the first negative culture also corresponds to the 'culture conversion' because *Mycobacterium tuberculosis* was not cultured based on the section 6.1 ① in the protocol.

- ④ Proportion of treatment success at the end of treatment
- ⑤ Proportion of relapse after treatment success
- ⑥ Proportion of death and time-to-death
- ⑦ Primary outcome evaluation between treatment groups according to pyrazinamide resistance

The secondary outcomes are analyzed as following and describe at exploratory levels.

1) Time To Sputum Culture Conversion After the initiation of treatment (Liquid and Solid Culture Media)

- In order to test whether the time to sputum culture conversion after initiation of treatment of the control arm and investigational arm (liquid and solid culture media) are different statistically, the median time is estimated in each group using the Kaplan-Meier method, and the difference of the distribution of time to culture conversion of the two arms is compared using the log-rank test.

2) Sputum Culture Conversion Proportion at Two Months of Treatment (Liquid and Solid Culture Media)

- In order to test whether there is a statistical difference in sputum culture conversion proportions at two months of the treatment between the control arm and the investigational arm (liquid and solid culture media), each arm is summarized by conversion frequency and proportion, and the proportion of sputum culture conversion at two months between the two arms are compared using the Chi-square test and Fisher's exact test.

3) Sputum Culture Conversion Proportion at Six Months of Treatment (Liquid and Solid Culture Media)

- In order to test whether there is a statistical difference in sputum culture conversion proportions at six months of the treatment between the control arm and the investigational arm (liquid and solid culture media), each arm is summarized by conversion frequency and proportion, and the sputum culture conversion proportion at six months between the two arms are compared using the Chi-square test and Fisher's exact test.

4) Proportion of Treatment Success at the End of Treatment

- Summarize the frequency and proportion of treatment success at the end of Treatment in the investigational arm.

5) Proportion of Relapse after Treatment Success

- Summarize the frequency and proportion of relapse after the treatment success in the investigational arm.

Relapse is defined as mycobacterium tuberculosis (MTB) is cultured again at least two or more consecutive times, taken at least 4 weeks apart, after treatment success (excluding re-infection confirmed by other strains).

6) Proportion of deaths and Time-to-Death

- Summarize the frequency and proportion of death in the investigational arm and estimates the median survival time using the Kaplan-Meier method.

7) Primary Outcome Evaluation Between Treatment Groups According to the Pyrazinamide Resistance

- Presentation of treatment success rate in the control arm and the investigational arm in small groups according to the presence or absence of Pyrazinamide resistance, and verification of non-inferiority of treatment success rate difference between the treatment groups.

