6.1. Culture Conversion to Negative

- i. Culture is considered to have converted to negative when two consecutive cultures, taken at least 4 weeks apart, are found to be negative.
- ii. When a subject cannot produce sputum after the first culture negative sputum, that is also defined as culture conversion.
- iii. Encourage to expectorate sputum as much as possible (including induced sputum), but if the subject cannot produce sputum, it will not be deemed as protocol violation.

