6.2. Date of Culture Conversion

For both the above i and ii, the date of culture conversion is defined as the date of the initial negative culture.

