Conversion (to negative): culture is considered to have converted to negative when two consecutive cultures, taken at least 30 days* apart, are found to be negative. In such a case, the specimen collection date of the first negative culture is used as the date of conversion. (*According to intervals of research visits, it will be 4 weeks)

Reversion (to positive): culture is considered to have reverted to positive when, after an initial conversion, two consecutive cultures, taken at least 30 days* apart, are found to be positive. For the purpose of defining Treatment failure, reversion is considered only when it occurs in the continuation phase. (*According to intervals of research visits, it will be 4 weeks)

7. Study Timeline

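### SAP 3.6.2 footnote 1 lets a contaminated culture confirm conversion, which protocol 6.1(i) does not allow; the effect on the secondary conversion endpoints is one-directional but probably small

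*Combined protocol and SAP*

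**What the plan says.** Protocol 6.1(i) defines conversion by two readable results: "Culture is considered to have converted to negative when two consecutive cultures, taken at least 4 weeks apart, are found to be negative". Note b to the outcome table in protocol 6.4 repeats this: "culture is considered to have converted to negative when two consecutive cultures, taken at least 30 days* apart, are found to be negative", with the interval adapted to 4 weeks for this trial's visits. Protocol 6.1(ii) gives the single exception: "When a subject cannot produce sputum after the first culture negative sputum, that is also defined as culture conversion". Under protocol 6.2, for both routes, "the date of culture conversion is defined as the date of the initial negative culture".

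Footnote 1 of SAP 3.6.2, attached to time to culture conversion, begins "The definition of 'culture conversion to negative' is per the protocol section '6. Definition". It continues "Contamination after the first negative culture also corresponds to the" conversion event, and gives as its reason that M. tuberculosis was not grown, citing item 1 of protocol 6.1.

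**The concern.** The footnote claims to apply the protocol definition but changes it. A contaminated culture yields no readable result. The footnote treats the absence of a positive as if it were a negative, whereas the clause it cites asks for a negative finding. Nor does 6.1(ii) cover the case, since a contaminated specimen is one that was produced.

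A participant with one negative and one unreadable culture is thus scored as a converter, dated at the first negative, with no second readable result. This feeds time to conversion (log-rank test) and the conversion proportions at two and six months (chi-square or Fisher's exact test), each on solid and liquid media. At stake is whether these endpoints measure what the protocol defines.

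**Working it through.** The plan gives no contamination rate and no expected conversion proportion, so there is no figure of its own to reproduce. The check has three steps.

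**1. Texts side by side.**
- Negative then negative, at least 4 weeks apart: conversion under protocol 6.1(i), 6.4 note b and the SAP.
- Negative, then no sputum can be produced: conversion under protocol 6.1(ii).
- Negative, then contaminated: conversion under the SAP footnote only; no protocol clause provides for it.
- SAP Table 8 lists Contaminated apart from Negative, Positive and Not done. That table covers pre-treatment cultures, so it shows only that contamination is recorded as its own result.

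**2. Direction.** Take a participant with a first negative culture. Let c be the probability that the second culture is contaminated, and p the probability that it would otherwise have grown M. tuberculosis.
- Confirmed under 6.1(i): (1 − c)(1 − p).
- Confirmed under the SAP: (1 − c)(1 − p) + c.
- Difference: exactly c, of which c × p would have been positive.

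With assumed c of 3-10% and p of 10-30%, c × p runs from 0.03 × 0.10 = 0.3% to 0.10 × 0.30 = 3% of participants with a first negative. The rule only adds qualifying pairs, so it cannot make conversion later or rarer.

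**3. Size.** I used a simulation with 200,000 patients per scenario. All inputs are assumptions: cultures every 4 weeks from week 4 to week 32; exponential time to true clearance with median 6 or 10 weeks; 10% or 30% of cultures falsely negative before clearance; contamination of 2%, 5% or 10% per culture. The comparator treats a contaminated culture as missing and requires the next readable one to be negative. Excess conversion under the SAP rule, in percentage points (range over the four clearance and false-negative scenarios):

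| Contamination | Week 8 | Week 24 |
|---|---|---|
| 2% | 0.08 to 0.28 | 0.05 to 0.26 |
| 5% | 0.15 to 0.68 | 0.13 to 0.66 |
| 10% | 0.30 to 1.22 | 0.28 to 1.29 |

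- Smallest case (median 6 weeks, 10% false negative, c = 2%): week 8, 61.90 − 61.82 = 0.08; week 24, 94.38 − 94.33 = 0.05.
- Largest case (median 10 weeks, 30% false negative, c = 10%): week 8, 52.60 − 51.38 = 1.22; week 24, 89.05 − 87.76 = 1.29.
- With the 48 evaluable participants per arm of protocol 10.1, the largest value is 48 × 0.0129 = 0.6 participant per arm.
- The SAP date was earlier than the comparator's in about 0.2% to 2.5% of patients and later in none.

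Between arms, suppose contamination is equal at 10%, false negatives are 30%, and one arm clears with median 6 weeks and the other with median 10. The week-8 difference is 66.98 − 52.60 = 14.38 points under the SAP rule and 66.31 − 51.38 = 14.93 under the comparator. The SAP rule narrows it by 0.55 points.

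**The case against.** The strongest reply is that little hangs on this. The endpoints are exploratory, the rule is prespecified and disclosed, and it is the same in both arms. Protocol 6.1(ii) already accepts a single negative when no second specimen exists, so two readable negatives are not an absolute requirement. Skipping a contaminated culture is itself a convention that the protocol does not spell out. All of this stands, and it limits the weight of the point. It does not remove the contradiction: the footnote invokes a clause that says something else, and its error has one direction.

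A reader might infer more in three ways, and the documents do not support any of them.
- **That the rule hides failures in the primary outcome**, because lack of conversion is one ground for failure in protocol 6.4. The footnote hangs on a secondary endpoint, and SAP 3.6.1 does not refer to it. Note b to 6.4 has its own definition with no contamination clause. Failure also requires that treatment was terminated or that at least two drugs needed permanent change. The documents do not expressly exclude the link, so clarification is warranted, but an effect is not shown.
- **That it biases the comparison between arms.** This needs contamination or culture positivity to differ by arm, and the documents give no evidence on either.
- **That the inflation is large.** Against a literal rule of two adjacent negatives, the same simulation gives 1.0 to 7.6 points at week 8. That rule would count a participant as unconverted merely because one tube was contaminated. It is not the change proposed here.

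**Conclusion.** The point holds for the secondary conversion endpoints. SAP 3.6.2 footnote 1 departs from the protocol definition it claims to follow, and it can only advance or increase conversion within an arm. The size cannot be determined from the documents. Under the assumed 2-10% contamination and the clearance patterns above, it is roughly 0.1 to 1.3 percentage points at weeks 8 and 24 compared with treating contamination as missing, which is less than one participant per arm. The simulation did not include the week-1 and week-2 cultures. The change is worth making before analysis because it is cheap and removes a plain inconsistency. The primary non-inferiority conclusion is not shown to depend on it.

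**What to change.** For the analyses in SAP 3.6.2, replace the footnote's second sentence with a rule on these lines:
- A contaminated culture is non-evaluable.
- Conversion requires that the next evaluable culture, taken at least 4 weeks after the first negative, is negative. If it is positive, that first negative does not count as conversion.
- If no sputum can then be produced, protocol 6.1(ii) applies as written.
- The conversion date stays at the first negative culture.

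Keep the present rule as a sensitivity analysis, and report contaminated cultures by arm, medium and visit so that readers can see whether contamination differs. Add one sentence stating that the footnote does not alter the conversion definition in protocol 6.4, and reconcile the SAP with protocol 6.1 and 6.4.

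The cost is one or two SAP sentences and a programming rule. Visits with cultures run every 4 weeks until week 52, or until the end of treatment in the investigational arm, so a later evaluable culture will usually exist. The downside is that a few participants will convert later or remain unconfirmed.
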